 - Help arrange logistics of DSMB meetings
 - Help prepare materials for DSMB meetings, including minutes of previous meeting, updated AE CRFs, and updated Data CRFs
 - Attend DSMB meetings
- c) Data Safety Monitoring Board
 - Convene via conference call before trial starts, to review protocol and decide on any amendments
 - Meet twice yearly via conference call to review trial progress, examine AE CRFs, examine Data CRFs, determine whether changes in the study are warranted, and determine whether the study should continue
 - Meet on emergency basis as determined by Chairperson
 - (Chairperson) Respond with recommendations within seven days to serious AEs reported by the Principal Investigator

• Adverse Events:

AEs as specified below occurring in the first 28 days after KP will be documented. An AE is defined as any unfavorable and unintended sign, symptom, laboratory finding, or disease temporally associated with the study, whether or not the AE is related to NAC therapy. These include events observed by the study team, reported by parents, and/or detected by laboratory findings. The following targeted AEs are reportable events in this study:

- a) Clinical AEs that are caused by NAC or likely caused by NAC (typically related to hypersensitivity and occurring at start of infusion):
 - Acute flushing
 - Skin erythema
 - Other rash
 - Urticaria

- Hypotension
- Tachycardia
- Edema
- Vomiting
- Wheezing
- Shortness-of-breath
- Bronchospasm
- Anapyhlaxis
- Redness/swelling/pain/bruising at intravenous line site
- Fluid infiltration at intravenous line site
- Vessel thrombosis at intravenous line site
- Infection at intravenous line site
- Loss of intravenous line
- b) Clinical AEs which could occur with BA in the first 28 days after KP, independent of therapy:
 - Increase in AST, ALT, and/or GGT >400 U/L above baseline (pre-KP) values (Note: in BA, baseline liver enzymes are already National Cancer Institute-Common Terminology Criteria for Adverse Events (CTCAE) Grade 3)
 - Increase in Bc >3 mg/dL above baseline (pre-KP) values (Note: in BA, baseline liver enzymes are already National Cancer Institute CTCAE Grade 3)
 - Increase in TB >5 mg/dL above baseline (pre-KP) values (Note: in BA, baseline liver enzymes are already National Cancer Institute **CTCAE** Grade 3)
 - Vomiting with feeds, requiring acid reduction therapy
 - Cholangitis, requiring antibiotic therapy
 - Infection of other etiology requiring treatment
 - Ascites
 - Diarrhea
 - Complications related to surgery
 - Death

• Serious AEs

Serious AEs, which are a subset of AEs as specified below, occurring at any time during the study period will be documented. In addition, serious AEs will be reported to the DSMB Chairperson within seven days of occurrence with the exception of events related to the management of the natural course of BA (i.e., hospitalizations for cholangitis, poor growth, worsening liver disease after failed KP, etc). After reporting a serious AE, the Principal Investigator and/or study team will receive recommendations about how to proceed with the study within seven days. Serious AEs are those AEs which:

- a) Result in death;
- b) Place the subject at immediate risk of death (does not include AEs which, if more severe, might have caused death);
- c) Require inpatient hospitalization or prolongation of existing hospitalization (with the exception of hospitalizations related to the natural course of BA, such as hospitalizations for cholangitis, poor growth, worsening liver disease after failed KP, etc)
- d) Lead to persistent disability which prevents a subject from conducting normal life functions; or
- e) In the first 28 days after KP, elevation of ALT >700 U/L above baseline, Bc 3x or >5 mg/dL above baseline, and/or TB 3x above baseline.
- Dose Modifications for AEs (including serious AEs) related to NAC infusion (based in part on a previously published protocol)³⁵

- a) Flushing alone, without pruritus, urticaria, or other serious signs
 - No intervention
 - Continue infusion, unless more severe signs develop
- b) Urticaria
 - \circ Stop infusion
 - Treat immediately with intravenous diphenhydramine (1.25 mg/kg/dose)
 - Restart infusion if symptoms resolve within 1 hour
- c) Angioedema, hypotension, wheezing (serious AE)
 - Stop infusion
 - Treat with intramuscular epinephrine (0.01 mg/kg/dose), diphenhydramine (1.25 mg/kg/dose), intravenous glucocorticoid (1 mg/kg/dose), and/or inhaled albuterol, at the discretion of the intensive care unit team
 - Do not restart infusion
 - Continue to follow patients for first two years of life, per study protocol
- d) Elevation of ALT >700 U/L above baseline, Bc 3x or Bc >5 mg/dL above baseline, and/or TB 3x above baseline (serious AE)
 - Stop infusion
 - Do not restart infusion
 - Follow patients clinically until elevated ALT/Bc stabilizes/resolves
 - Evaluate for drug-induced liver injury if deemed appropriate by the clinical team, based on FDA recommendations

(https://www.fda.gov/downloads/Drugs/.../guidances/UCM174090.pdf)

Reporting

AEs (serious and non-serious) occurring in the first 28 days will be recorded on CRFs and presented to the DSMB at each meeting. In addition, serious AEs occurring at any time during the study period will be reported directly to the Chairperson within seven days of occurrence with the exception of events related to the management of the natural course of BA (i.e., hospitalizations for cholangitis, poor growth, worsening liver disease after failed KP, etc). This reporting schedule is designed to help the DSMB decide whether the trials meets sufficient safety standards to continue. AE CRFs will have describe each AE using the following categories (see sample AE ORF):

- a) Category of AE
 - AEs will be categorized into pre-determined groups, as specified by the CTCAE.
 - These groups include Anemia, Cardiovascular, Congenital, Death, Dermatological, Febrile events, Gastrointestinal, Gynecological, Hematological, Hepatic, Injury, Immunological, Infectious viral, Infectious cholangitis, Infectious surgical, Infectious, Investigation (laboratory results), Metabolic, Miscellaneous, Musculoskeletal, Neoplastic, Neurological, Nutritional, Orthopedic, Pulmonary, Surgical, Urinary, Wound non-infectious, IV Issues
- b) Severity of AE Serious or non-serious
- c) Description of event Concise description of AE, including date occurred
- d) Grading of AE
 - CTCAE grade will be used, in accord with CTCAE Version 5.0
 - If the CTCAE does not have a grading for a particular AE, the severity of the event should be
 reported based on the following (this is independent of an AE designated as serious, which requires
 prompt reporting to the DSMB Chairperson):
 - Grade 1: Asymptomatic or mild symptoms, clinical or diagnostic observations only; intervention not indicated.
 - o Grade 2: Moderate; minimal, local, or noninvasive intervention indicated
 - Grade 3: Severe or medically significant but not immediately life-threatening; hospitalization or prolongation of hospitalization indicated; disabling. (As mentioned above, liver enzymes will be

Grade 3 at baseline, so only AST, ALT, and/or GGT >400 U/L above baseline and/or Bc >3 mg/dL above baseline will be reported as an AE. If this were to occur, the AE would be Grade 3)

- Grade 4: Life-threatening consequences; urgent intervention indicated.
- Grade 5: Death related to AE.
- e) Relationship to NAC
 - Related: There is clear evidence that the event is related to the use of study drug (i.e., rash with NAC infusion)
 - Possible: The event cannot be explained by BA, other therapies, or other causes, and these is a plausible temporal relationship between the event and NAC administration
 - Unlikely/Remote: An event for which an alternative explanation is more likely or the temporal relationship to NAC administration does not support a causal relationship
 - Not related: The event can readily be explained by BA, other therapies, or other causes, and therefore the Principal Investigator believes no relationship exists between the event and NAC therapy
- f) Action Taken with Study Drug
 - None: No changes made to NAC administration
 - Discontinued: Study drug was discontinued
- g) Treatment Given for AE A list of any treatments or procedures given for the event.
- h) Outcome of the AE
 - Ongoing: AE persists despite intervention
 - Recovered: Subject recovers completely from AE
 - Change in severity: AE became serious from non-serious or vice versa
 - Unknown
 - Death
- Review of AEs

The DSMB will review all AE CRFs at biannual meetings and review serious AEs if an emergency meeting is called by the DSMB Chair. The DSMB will then decide if the study should be stopped for safety reasons.

• Data Management, Analysis, and Quality Assurance

The DMSB will review enrollment, enrollment targets, and findings recorded for each subject to ensure the validity and integrity of the data. At each DSMB meeting, updated Data CRFs for each subject will also be presented (see sample Data CRF). The DSMB will assure quality assurance, defined as "All those planned and systematic actions that are established to ensure that the trial is performed and the data are generated, documented (recorded), and reported in compliance with Good Clinical Practice (GCP) and the applicable regulatory requirement(s).

Sample Adverse Event (**AE**) Clinical Report Form (**CRF**)

:	Category ¹	Description	SAE?	Grade (CTCAE) ²	Start Date	Outcome ³	End Date	Relationship to NAC ⁴	Action Taken with NAC⁵	Treatment Given	Investigator Initials/Date

Participant ID:

¹ Category of AE:	² Grading of AE (Only If NOT in CTCAE)	³ Outcome of the AE:	⁴ Relationship to NAC:	⁵ Action Taken with NAC:
Anemia, Cardiovascular, Congenital, Death,	Grade 1 – Asymptomatic or mild symptoms; clinical	1 - Ongoing; AE continues	1 - Related	N - none; no changes
Dermatological, Febrile events, GI, Gynecological,	or diagnostic observations only; intervention not	despite intervention	2 - Possible	made to NAC
Hematological, Hepatic, Injury, Immunological,	indicated.	2 - Recovered; subject recovers	3 - Unlikely/Remote	administration
Infectious Viral, Infectious Cholangitis, Infectious	Grade 2 – Moderate; minimal, local, or noninvasive	completely from AE	4 - Not Related	D - Study drug
Surgical, Infectious, Investigation (lab results),	intervention indicated.	3 - Change in severity; AE		discontinued
Metabolic, Miscellaneous, Musculoskeletal,	Grade 3 – Severe or medical significant but not	became serious from non-		
Neoplastic, Neurological, Nutritional, Orthopedic,	immediately life-threatening;, hospitalization or	serious or vice versa		
Pulmonary, Surgical, Urinary, Wound Non-Infectious,	prolongation of hospitalization indicated; disabling.	4 - Unknown		
IV Issues	Grade 4 – Life-threatening consequences; urgent	5 - Death		
	intervention indicated.			
	Grade 5 – Death related to AE.			

Sample Data Clinical Report Form (CRF)

Participant ID:

Gender:	Episodes of cholangitis (and days after KP):
Race:	Episodes of ascites (and days after KP):
Ethnicity:	Episodes of variceal bleed (and days after KP):
Gestation Age:	Liver transplant listing (days after KP):
Age at KP:	Liver transplant (days after KP):

	Pre-	D	ays Post	-KP				Weeks F	Post-KP			Mo	onths of L	ife	
	KP	3	7	10		2	4	8	12	18	24	12	18	24	
TSBA					_										
Вс															
AST															
ALT															
GGT															
Alb															
Na															
T Bili															
Plt					•										
INR															
Vit D															
Vit A															
Vit E															
Wt															
Wt Z															

Data and Safety Monitoring Board Charter

Study: A Phase 2 Trial of N-Acetylcysteine in Biliary Atresia after Kasai Portoenterostomy **PI:** [name] PhD **Institution:** Baylor College of Medicine and Texas Children's Hospital

The Data and Safety Monitoring Board (**DSMB**) will act in an advisory capacity to monitor participant safety, data quality and evaluate the progress of the study.

DSMB Responsibilities

- Review the research protocol, informed consent documents and plans for data safety and monitoring prior to enrollment of the first study participant;
- Evaluate the progress of the trial, including periodic assessments of data quality and timeliness, recruitment, accrual and retention, participant risk versus benefit, and other factors that can affect study outcome;
- Consider factors external to the study when relevant information becomes available, such as scientific
 or therapeutic developments that may have an impact on the safety of the participants or the ethics of
 the trial;
- Review study performance, make recommendations and assist in the resolution of problems reported by the Principal Investigator;
- Protect the safety of the study participants;
- Make recommendations concerning continuation, termination or other modifications of the trial based on the observed beneficial or adverse effects of the treatment under study;
- Review interim analyses in accordance with stopping rules, as defined in the protocol for the two-stage "minimax" trial design;
- Ensure the confidentiality of the study data and the results of monitoring; and,
- Comment on any problems with study conduct, enrollment, and/or data collection.

The DSMB will discharge itself from its duties when the last participant completes the study.

Membership

The DSMB consists of three members (two members constitute a quorum). The members will include two clinicians with expertise in pediatric hepatology and one pediatric hospital-based pharmacist, each from an institution unaffiliated with the study site. Members will have no financial, scientific, or other conflict of interest with the trial, including no ongoing collaborations with the Principal Investigator. Written documentation attesting to absence of conflict of interest is required (see below).

The Chairperson of the DSMB is responsible for overseeing the meetings and developing the agenda in consultation with the Principal Investigator. The Chair is the contact person for the DSMB. The Chair is also the safety officer, and will be the contact person for serious adverse event reporting.

In the event that a member or Chairperson has to leave, the Principal Investigator will be responsible for finding a new member within 28 days. During the vacancy of a Chairperson, the other clinician member of the DSMB will serve as Chairperson until a new one is recruited.

Meeting Format

All meetings will be performed by conference calls organized by the study team. At the first meeting, the DSMB will review the protocol and guidelines for how the board will monitor the study. Subsequently, DSMB meetings will be held at least two times per year, starting three months after the first subject is enrolled. In addition, the Chair can call an emergency meeting at any time should participant safety questions or other unanticipated problems arise.

Meetings will consist of two sessions. The first session will be attended by the Principal Investigator and key members of the study team. The second session will occur without the Principal Investigator and key members of the study team. Discussion in both sessions will focus on the conduct and progress of the study, including participant accrual, protocol compliance, and problems encountered. Each meeting must include a recommendation to continue or to terminate the study (made by a majority vote) and whether the DSMB has any concerns about participant safety.

Communication

Immediately after each DSMB meeting, the Chair will call the Principal Investigator and study team to discuss the DSMB's recommendations. The study team will record the DSMB's recommendations in a "Minutes" document, to be approved before starting the subsequent meeting.

At any time during the study, the Principal Investigator will inform the Chair about serious adverse events via email no later than seven days after the event. The Chair, at his/her discretion, may choose to share the email with the other members. The Principal Investigator is responsible for soliciting a response from the Chair within seven days after the initial email is sent, to determine if any further action is necessary. The study staff will save these emails in the study file, and present them at the next DSMB meeting.

Meeting Materials

Materials will be prepared by the study staff, and provided in electronic form to the DSMB members at least seven days before the meeting. They will include:

- Approving Minutes from previous meeting
- Summary of interim events, including updates on (i) safety data, (ii) problems encountered, (iii) total enrollment, and (iv) primary outcome results
- All Adverse Event Case Report Forms (interim updates highlighted in a different color)
- Any interim email communications between Chair and Principal Investigator regarding serious adverse events
- Copy of the study protocol, including any new updates

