NAC has a number of properties that make it an especially attractive potential therapeutic agent. First, glutathione creates an osmotic gradient in the bile duct lumen which drives one-third of total bile flow in humans (the other drivers are bile acids and secretin/bicarbonate).^{7–9,14} Second, NAC is a Food and Drug Administration-approved therapy for another serious liver condition in neonates and children (acetaminophen overdose).¹⁵ It has also been used for other liver and non-liver indications in

Table: Other Studies Using IntravenousNAC in Neonates

Liver-related

- Parenteral nutrition associated cholestasis^{16,17}
- Nonacetaminophen acute liver failure^{18,19}
- Neonatal hemochromatosis (gestational alloimmune liver disease)²⁰
- Liver-unrelated
- Bronchopulmonary dysplasia²¹
- Chorioamnionitis^{22,23}

neonates, with few reported adverse events (Table).^{16–23} Third, glutathione is an anti-oxidant, which could

scavenge the free radicals contributing to cirrhosis. Fourth, glutathione is catalyzed into glycine, glutamate, and cysteine by gamma-glutamyl transferase (**GGT**), thereby potentially fulfilling a nutritive role for cholangiocytes.^{14,24,25} Preclinical studies are also promising, with glutathione's strong choleretic properties best established in rat flow studies and NAC's hepatoprotective effects documented in rescuing different mouse models of cholestasis.^{14,26–28}

To test our hypotheses, we will administer intravenous NAC continuously for seven days and determine the number of subjects with normal TSBAs (0-10 umol/L) within 24 weeks of KP. In addition, markers of BA progression, such as abnormal laboratory results, failure-to-thrive, and occurrence of complications related to chronic liver disease, will be described over the first two years of life. Finally, all adverse events occurring during NAC infusion and in the 21 days after its completion will be recorded. Our study employs the two-stage "minimax" Phase 2 clinical trial design, a design commonly used in oncological trials to determine whether a particularly therapy has sufficient activity to warrant a larger Phase 3 trial.²⁹ The two-stage "minimax" design offers two distinct advantages compared to other designs: (i) early termination if the drug is not efficacious; and (ii) small sample sizes, because historical controls rather than a separate control arm are used.

C. Enrollment Procedures

- i. Inclusion Criteria (all must be met)

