to have low Vitamin A levels (<20 mcg/dL), intramuscular Vitamin A injections of 50,000 IU will be given two days before KP and 28 days after KP. Steroids will not be used as standard post-KP care.

b) Experimental therapies: No other investigational therapies will be given during the study period.

viii. Removal of Patients from Study

- a) Parents may voluntarily exclude their infant from the study at any time
- b) The investigators may remove a patient if the study team decides that continuation is not in the best interest of the participant of the study (i.e., patient receives another experimental therapy during the two-year study period that will confound the results).

E. Data Collection

- i. Clinical Data All clinical data (laboratory results, weights, occurrence of sentinel events) will be stored in the patient's electronic medical record. In addition, a comprehensive study form containing all data for each subject will be updated as new results become available.
- ii. Adverse Events All adverse events (observed by the study team, reported by parents, and/or detected by laboratory findings) will be recorded in the patient's medical record as well as separate form specifically for the study. The form will be submitted to the DSMB following a pre-determined schedule (see DSMP in Appendix).

F. Statistical Considerations

i. Overview

This is a Phase 2 clinical trial using the two-stage "minimax" design described by Simon.²⁹ As a Phase 2 trial, the trial's objective is to determine whether NAC

has sufficient biological activity as adjunctive therapy for BA to warrant further study. By choosing the two-stage "minimax" design, we gain two advantages: (i) early termination if the drug is not efficacious, and (ii) using historical controls and therefore an overall smaller sample size to test the hypothesis, i.e., no randomization or control arm. This study design only identifies large effects (response >20%). For BA this is appropriate, because the field is in need of a robust therapy that can substantially limit liver damage and delay/prevent need for liver transplantation.

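### The Data and Safety Monitoring Plan ties adverse-event documentation to a 27-item list, Sections B and E.ii record all adverse events, and pruritus, a named outcome, is not on the list

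*Combined protocol and SAP*

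**What the plan says.** The scope of AE recording is stated in several places.

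- **Section B (Background and Rationale):** "all adverse events occurring during NAC infusion and in the 21 days after its completion will be recorded".
- **Section E.ii (Adverse Events):** "All adverse events (observed by the study team, reported by parents, and/or detected by laboratory findings) will be recorded". On the study form it adds: "The form will be submitted to the DSMB following a pre-determined schedule".
- **DSMP, Adverse Events:** "AEs as specified below occurring in the first 28 days after KP will be documented". A broad definition of an AE follows, covering any untoward sign, symptom, laboratory result or illness in time with the study, whether or not NAC caused it. The paragraph then closes with "The following targeted AEs are reportable events in this study" and gives two lists: (a) events attributed to NAC and (b) events expected in biliary atresia.
- **DSMP, Reporting:** "AEs (serious and non-serious) occurring in the first 28 days will be recorded on CRFs and presented to the DSMB at each meeting". This sentence does not mention the list. The AE categories that follow include neurological, metabolic, hematological and laboratory-investigation groups.
- **Section D.v (secondary outcomes):** names nine AE outcomes possibly related to NAC, pruritus among them, and refers to the DSMP.

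The DSMP also states liver-test thresholds for reporting in two places. List (b) has three entries, one of which is "Increase in TB >5 mg/dL above baseline (pre-KP) values". The grading text under Reporting says that "only AST, ALT, and/or GGT >400 U/L above baseline and/or Bc >3 mg/dL above baseline will be reported as an AE".

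**The concern.** Objective 5 is to document AEs that may be associated with NAC, and Section D.v sends staff to the DSMP for them. There they meet a targeted list described as the reportable events. Sections B and E.ii describe a different rule. A study coordinator cannot follow both, and the plan does not say which prevails.

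If the list prevails, a non-serious event outside it need not be entered on the AE form. It would then have no CTCAE grade and no assessment of relationship to NAC, and it would be missing from the safety tables. In a single-arm trial of at most 16 planned infants, a reader of the final report could not tell whether a zero count means that none occurred or that the event was not collected.

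**Working it through.** The plan gives no figure on this point, so the check is a comparison of the texts with a few counts.

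**1. Are the time windows the same?** Section B covers the infusion plus 21 days: 7 + 21 = 28 days. The DSMP covers 28 days after KP. The infusion starts within 24 hours of KP, so the two windows end within about a day of each other. The conflict concerns scope, not time.

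**2. How long is the list?**
- List (a): 12 general events (flushing through anaphylaxis) + 5 intravenous-line events = 17.
- List (b): 3 liver-test entries + 7 clinical entries = 10.
- Total: 17 + 10 = 27.

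There is no general entry for other events. The open entries for other rash and other infection extend only their own category.

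**3. Does the list cover the AE outcomes in Section D.v?** The nine outcomes are rash, urticaria, pruritus, tachycardia, hypotension, vomiting, edema, anaphylaxis and intravenous-line issues. Eight of the nine have a counterpart in list (a); pruritus does not.

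**4. Which other events named in the protocol are unlisted?** Examples:
- hyponatremia leading to seizures, and effects on coagulation and platelet aggregation (Section H.iv);
- nausea, rhinorrhea, cough, stridor and dizziness (Section H.iv, formulary summary);
- stomatitis (Section G.ii);
- bradycardia (Section D.iv, in a cited study).

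Angioedema is also absent from the list, although the DSMP's dose-modification text labels it a serious AE. I give no total, because it would depend on how overlapping terms are grouped.

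**5. What happens to a non-serious event outside the list?**

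| Event | If all AEs are recorded | If the list governs |
|---|---|---|
| Pruritus | AE form, grade, relationship | No AE form; no Data CRF field |
| Seizure | AE form, grade, relationship | No AE form; no Data CRF field |
| Low sodium | AE form, grade, relationship | Value on Data CRF only |
| INR or platelet change | AE form, grade, relationship | Value on Data CRF only |

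**6. Do the liver-test thresholds agree?** List (b) has three: AST/ALT/GGT above baseline by more than 400 U/L, conjugated bilirubin (Bc) by more than 3 mg/dL, and total bilirubin (TB) by more than 5 mg/dL. The restrictive sentence under Reporting repeats the first two and leaves out TB. This mismatch remains whichever way the list is read.

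**7. How ambiguous would a zero count be?** The chance of at least one case in 16 infants is 1 − (1 − p)^16. The documents give no rate for the unlisted events, so p is an assumption:
- p = 0.05: 1 − 0.95^16 = 0.560
- p = 0.10: 1 − 0.90^16 = 0.815
- p = 0.20: 1 − 0.80^16 = 0.972

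Over this assumed range an event has a better than even chance of occurring at least once, so whether it is collected could change what is reported.

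**The case against.** The strongest reply is that the list was never meant to be closed. The AE definition comes directly after the sentence that ties documentation to what is specified further down, so that pointer may refer to the definition, with the list as a targeted subset. The wording of Section E.ii on how events come to light closely matches the DSMP sentence after the definition, which suggests one intended scope. The AE form has categories with no obvious counterpart among the 27 items, and the DSMP supplies fallback grades for events without a CTCAE grade. A sentence restricting only the liver tests is most natural if other AEs are reported generally. All of this stands, and it makes the all-AE reading the better one. It does not remove the statement that the targeted events are the reportable ones, so the DSMP remains at odds with itself.

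Existing routes also limit the damage. Serious cases go to the board's Chair within seven days, apart from events in the natural course of biliary atresia. Section D.vi(e) provides for an emergency board meeting after a severe related or possibly related event during infusion. Prolonged hospitalization makes an event serious, and the usual stay of 10–14 days covers the infusion, so a non-serious seizure in that period is a narrow case. Listed items such as surgical complications or line-site bruising could capture some bleeding. These points stand, with one reservation: the opening of the Serious AEs text can be read as pointing to the seriousness criteria or to the targeted list.

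A footnote to the observation schedule cites a Table 4 for laboratory AEs. That table is not in the text reviewed, so its coverage cannot be checked and nothing here rests on it.

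**Conclusion.** The inconsistency is real and should be corrected, but its reach is modest. Two statements (Sections B and E.ii) record all AEs, while one DSMP paragraph points to 27 targeted events and calls them reportable. The one demonstrable gap against the protocol's own outcomes is pruritus, 1 of 9 in Section D.v. The separate TB mismatch, three thresholds against two, stands on its own.

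Three stronger conclusions are tempting, and the documents do not support them:
- **That AE capture is definitely restricted to the list.** The broad definition and the AE form categories point the other way.
- **That hyponatremia and coagulation effects would go unseen.** Sodium, INR and platelets are on the Data CRFs presented at each board meeting. Section H.iv also says that the single dilution follows the approved instructions and that NAC did not affect blood loss in the cited study, and infants with INR above 1.3 despite vitamin K are excluded.
- **That a few named events make up the whole gap.** Many other side effects mentioned in the protocol are unlisted too, so adding a handful would not close it.

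Under-recording follows only if staff treat the list as governing. The primary analysis is unaffected on either reading.

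**What to change.** Reconcile Sections B, D.v and E.ii with the DSMP texts on Adverse Events, Serious AEs and Reporting:

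1. State one scope: all AEs in the first 28 days after KP, as Sections B and E.ii already say.
2. Keep the DSMP list, but describe it as examples or solicited events, and add pruritus so that it matches Section D.v.
3. Keep the existing above-baseline reporting thresholds for liver tests as an explicit exception, and make the list and the grading text agree on whether TB is among them.
4. In the Serious AEs text, say that the pointer refers to the seriousness criteria, so that an event outside the list can still be serious.

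If follow-up has already ended, the report on Objective 5 should state which scope was applied.

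The cost is wording changes and somewhat more AE forms. The added laboratory screening is small. With 16 infants and five post-KP columns up to week 4 (days 3, 7 and 10; weeks 2 and 4), there are at most 16 × 5 = 80 scheduled results per analyte. That is a ceiling on scheduled draws, because the marks in the schedule are not visible in the text; unscheduled draws or replaced subjects would add to it. No clinical threshold or management rule is proposed.
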